10.7 Medical Monitor

An independent Medical Monitor will be responsible for individual and timely review of adverse events as defined below. The Medical Monitor will be a physician with relevant therapeutic and medical expertise that is not participating as an Investigator in the study and does not have a financial, scientific, or other conflict of interest with the clinical study.

Specific responsibilities of the Medical Monitor include:

- Review of all adverse events reported during the study
- Review all serious study procedure-related and/or investigational device-related adverse events to determine if the adverse event warrants consideration as a UADE and facilitate the reporting of UADEs if applicable
- Adjudicate the following(a) all SAEs; (b) any events of Diabetic Ketoacidosis or Severe Hypoglycemia; (c) all AEs reported by the site as related or

possibly related to the investigational device; and/or (d) any additional events as requested by the Sponsor.

- The specified events will be adjudicated to determine:
 - event relatedness to the study procedures and/or the investigational device
 - event categorization and assess seriousness and severity
 - whether an adverse event is anticipated or unanticipated

The adjudication decision of the Medical Monitor will be used for the final classification of events, including relatedness to the study procedures and/or the investigational device, for the determination of safety endpoints and for all regulatory reports, product labeling, and publications or presentations.

The study Medical Monitor will review all adverse events and adverse device events that are reported during the study. SAEs will typically be reviewed within 24-hours of reporting. Other AEs will typically be reviewed approximately weekly.

The Medical Monitor's roles and responsibilities are described in the Safety Management Plan (SMP).

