10.6.2 Criteria for Suspending or Stopping Overall Study

Study activities will be suspended if the manufacturer of any component of the investigational study device requires stoppage of device use for safety reasons (e.g. product recall).

The affected study activities may resume if the underlying problem can be corrected by a protocol or system modification that will not invalidate the results obtained prior to suspension.

The study Medical Monitor will review all adverse events that are reported during the study. The Medical Monitor may recommend suspension of study activities or stoppage of the study to the Sponsor if deemed necessary based on the totality of safety data available.

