11.6 Safety Analyses

11.6.1 Evaluation of Adverse Events

All adverse events reported over the course of the study will be summarized and tabulated by study phase, event category, seriousness, severity, and relationship to the study and the investigational device. For the purposes of summarization, an event will be considered “Related” if the relationship was deemed as “Possibly Related” or “Related”. In cases where the same event is reported more than once per subject, the event will only be counted once in the incidence table(s).

Adverse events leading to death or to discontinuation from the study will be listed separately. A listing of all adverse events will be provided.

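### For non-serious AEs, adjudication under 10.7 can lower the device-related count but can raise it only if the sponsor asks

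*Combined protocol and SAP*

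**What the plan says.** Under 10.3.5 the site investigator rates each AE as unrelated, possibly related or related, both to study procedures and to the device. Section 10.7 then defines what the Medical Monitor adjudicates: "Adjudicate the following(a) all SAEs; (b) any events of Diabetic Ketoacidosis or Severe Hypoglycemia; (c) all AEs reported by the site as related or". Item (c) goes on to include a possible link as well, and it is limited to the device. Item (d) adds "any additional events as requested by the Sponsor". Among the things adjudication decides is "event relatedness to the study procedures and/or the investigational device".

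The result is binding: "The adjudication decision of the Medical Monitor will be used for the final classification of events". Section 10.7 applies this to safety endpoints, regulatory reports, labeling and publications.

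Review is a separate and wider duty. Section 10.6.2 says "The study Medical Monitor will review all adverse events that are reported during the study", and 10.7 repeats it, with non-serious events seen roughly weekly. Neither section says that review alone can change a rating.

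Section 11.6.1 tabulates AEs by, among other things, "relationship to the study and the investigational device", pooling possibly related with related, and provides a listing of every AE.

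**The concern.** For non-serious events, the trigger for independent adjudication is the same site rating that adjudication is meant to check. False positives go to an adjudicator who can remove them. False negatives do not, unless the sponsor chooses to refer them. A filter of this shape pushes the count in one direction, and the only stated adjudication route in the other direction is at the discretion of the party whose device is being studied.

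The events exposed are reportable non-serious AEs that the site rates unrelated to the device: hyperglycemia or ketosis short of DKA, AEs with an emergency-department visit, and AEs tied only to a study procedure. Wrong unrelated ratings are conceivable because the guidance in 10.3.1 pulls two ways on user error. A note to the ADE definition counts events resulting from user error. The paragraph after it says that events due solely to user error will generally not count unless the instructions or manual may have contributed. For a bolus calculator that the user operates, sites may have to make that judgment.

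At stake is whether the non-serious device-related counts, which 10.7 carries into regulatory reports and labeling, have been checked for errors in both directions.

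**Working it through.** The plan states no figure on this point, so there is none to reproduce. The direction follows from the text; the size needs assumptions.

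**Step 1: routes open to a non-serious AE.** Item (a) covers SAEs. Item (b) covers DKA and severe hypoglycemia, which 10.3.4 and 10.3.3 already treat as SAEs, so it adds no non-serious route. Only (c), the site's device rating, and (d), sponsor request, remain.

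**Step 2: every case.** Possibly related and related are pooled, as in 11.6.1.

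| Event | Site device rating | Sponsor request | Adjudicated | Device-related status can move |
|---|---|---|---|---|
| Serious | Unrelated | Either | Yes | Up |
| Serious | Possibly related or related | Either | Yes | Down |
| Non-serious | Possibly related or related | Either | Yes | Down |
| Non-serious | Unrelated (including procedure-only) | Yes | Yes | Up |
| Non-serious | Unrelated (including procedure-only) | No | No | Fixed |

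Without a sponsor request, the adjudicated non-serious device-related count cannot exceed the site's count. For serious events both directions are open.

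**Step 3: size.** Let N be the number of reported non-serious AEs, p the share truly device-related, and Se and Sp the site's sensitivity and specificity. Assume that the adjudicator is always correct and the sponsor makes no request.

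- Site ratings alone: N[p·Se + (1−p)(1−Sp)]
- Current rule: N·p·Se, because all false positives are removed and all false negatives stay
- All adjudicated: N·p
- Proportional undercount under the current rule: 1 − Se, whatever Sp is

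An illustration with N = 20, p = 0.5 and Sp = 0.8. All are assumptions; the documents give none of them.

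| Se | Site alone | Current rule | All adjudicated | Undercount |
|---|---|---|---|---|
| 0.70 | 7 + 2 = 9 | 7 | 10 | 30% |
| 0.80 | 8 + 2 = 10 | 8 | 10 | 20% |
| 0.95 | 9.5 + 2 = 11.5 | 9.5 | 10 | 5% |
| 1.00 | 10 + 2 = 12 | 10 | 10 | 0% |

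At Se = 0.80 the site-alone count equals the true count only because p = 0.5 and Se = Sp make the two kinds of error cancel.

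**Step 4: few events.** If only 3 events are truly related and Se = 0.8, the expected number missed is 3 × 0.2 = 0.6. The chance of missing at least one, taking ratings as independent, is 1 − 0.8³ = 0.488, about 49%.

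**The case against.** The strongest defense is that this is a sensitive screen followed by a specific check, which is a reasonable design. Section 10.3.5 sets a low bar for Possibly Related, and either that or Related triggers adjudication. A site following the definition would seldom rate a plausible device event as outright unrelated, so sensitivity could be close to 1 and the undercount close to nothing. This stands as a limit on size, not on direction.

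The most obvious exposed event is also partly protected. For unexplained hyperglycemia with meter glucose of at least 300 mg/dL and ketones above 1.0 mmol/L, 10.2 already directs suspicion to an occlusion or dislodged cannula, that is, to the Pod. A rating of at least possibly related would be natural there. Reportable hypoglycemia is fully covered, because 10.3.3 makes it reportable only when it is severe or results in an SAE. Both points stand.

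A reader might infer that a site's unrelated rating can never be raised. The documents do not support that. The Medical Monitor sees every AE and could query a site, the investigator could revise a rating, and the sponsor could refer the event under (d). Section 10.7 also places the Monitor's duties in the Safety Management Plan, which is not among the documents and might add a route. What remains is that 10.7 gives review no stated power to reclassify and requires none of these steps.

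A reader might also infer that the trial's main safety result is biased. It is not: the primary endpoints are CGM percentages of time below 70 and above 180 mg/dL, which do not use AE ratings. The AE tables are descriptive, the study is not powered (11.2), and unadjudicated events still appear in the listing.

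**Conclusion.** The point holds in a limited form. As written, 10.7 makes adjudication of non-serious AEs one-directional for device relatedness unless the sponsor intervenes. That rests on the text alone and needs no assumed figures. It affects only the non-serious device-related counts in 11.6.1; the total can still rise through serious events.

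The size cannot be established from the documents. It equals 1 minus site sensitivity if the adjudicator is correct: 5% to 30% over the assumed range 0.95 to 0.70, and less if sites apply the inclusive definition well. With up to 42 subjects followed for 14 days and the narrowed reporting criteria of 10.3.2, the practical difference may be zero or one event. The case for change is that the asymmetry is unnecessary and cheap to remove, not that a large error has been shown. The conclusion would weaken if the Safety Management Plan already provides an upward route.

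**What to change.** In 10.7, replace item (c) with: *all other reportable AEs, whatever relatedness the site assigned*, and state that relatedness to both device and procedures is adjudicated for each. Carry the same wording into the Safety Management Plan. If that plan already contains such a route, 10.7 should say so.

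In 11.6.1, tabulate relatedness as rated by the site and by the Medical Monitor side by side, with the adjudicated rating remaining final, so that changes in either direction are visible.

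Do not count an event as related whenever either party says so. That keeps every site false positive: with the illustrative inputs above, 10 + 10 × 0.2 = 12 against a true 10, a 20% overcount. It would also contradict the finality sentence in 10.7.

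The cost is one changed item in 10.7, a matching line in the Safety Management Plan, a few more adjudication forms and one extra table column. The Medical Monitor already reviews every AE, so no new reviewer is needed.

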11 STATISTICAL CONSIDERATIONS

11.1 General Statistical Methods

Standard statistical methods will be employed to analyze all data. All data collected in this study will be documented using summary tables and subject data listings. Continuous variables will be summarized using descriptive statistics, including counts, mean, median, standard deviation (SD), minimum and maximum. Where appropriate, 95% two-sided confidence intervals for the means or medians will be presented. If the observed data are found not to follow a normal distribution, appropriate non-parametric methods may be employed. Categorical variables will be summarized by frequencies and percentages. Unless explicitly stated otherwise, percentages will utilize a denominator corresponding to the number of unique subjects.

Data from different centers will be pooled for all analyses. Data will be summarized by age cohort.

As subjects aged 6-70 years are expected to complete the study prior to the start of enrollment of subjects aged 2-5.9 years, two separate clinical reports will be generated.

11.2 Sample Size

This is a non-powered, single-arm, multi-center, observational study. The sample size for the study is not hypothesis-driven and has been chosen to gather adequate clinical data on the performance of the Omnipod Horizon™ System's CGM-informed bolus calculator and summarize its safety profile.

Up to 42 subjects may be enrolled in the study cross 4-7 clinical study sites in order to obtain approximately 30 evaluable subjects. The evaluable subjects will be comprised of three age cohorts as follows:

- 15 subjects aged 18-70 years
- 10 subjects aged 6-17.9 years
- 5 subjects aged 2-5.9 years

11.3 Objectives and Endpoints

11.3.1 Primary Objective

The primary objective of this study is to evaluate the safety of the Omnipod Horizon™ System's CGM-informed bolus calculator in patients with type 1 diabetes during Manual Mode operation.

11.3.2 Primary Endpoints

The primary objective will be to evaluate the safety of the CGM-informed bolus calculator (Phase 2) using the following endpoints as measured by the system CGM:

Glucose metrics during the 4-hour post bolus period from Phase 2 will be compared to Phase 1:

- % of time < 70 mg/dL
- % of time > 180 mg/dL

11.3.3 Secondary Objective

The secondary objective of this study is to evaluate additional glycemic measures of effectiveness of the Omnipod Horizon™ CGM-informed bolus calculator during Manual Mode operation.

11.3.4 Secondary Endpoints

The secondary objective will be evaluated using the following per subject effectiveness endpoints:

Glucose metrics during the 4-hour post bolus period from Phase 2 will be compared to Phase 1:

- Mean glucose
- % of time < 54 mg/dL
- % of time \geq 250 mg/dL
- % of time \geq 300 mg/dL
- % of time in range 70-180 mg/dL

Glucose metrics from Phase 2 will be compared to Phase 1 during the day (6AM up to 12AM), overnight (12AM up to 6AM), and overall:

- Mean glucose

- % of time < 54 mg/dL
- % of time < 70 mg/dL
- % of time > 180 mg/dL
- % of time \geq 250 mg/dL
- % of time \geq 300 mg/dL
- % of time in range 70-180 mg/dL
- % of time in range 70-140 mg/dL
- Standard deviation
- Coefficient of variation

11.4 Analysis Sets

The following analysis sets are planned for the study:

11.4.1 ITT (Intention to Treat) Analysis Set

The ITT analysis set includes all subjects that are enrolled in the study. All safety analyses (other than primary analysis of primary endpoints) will be based on the ITT analysis set.

11.4.2 mITT (modified Intention to Treat) Analysis Set

The modified Intention to Treat (mITT) analysis set is a subset of the ITT analysis set. The mITT analysis set will consist of subjects who have entered the Manual Mode with a connected CGM phase of the study (Phase 2) successfully. The mITT analysis set will be used as the primary analysis for the primary and secondary endpoints and other clinical outcome data.

11.4.3 PP (Per-Protocol) Analysis Set

The Per-Protocol (PP) analysis set is a subset of the mITT analysis set. Subjects will be included in the PP analysis set if they have a minimum of 80% system use (approximately 5.6 days) during Phase 2 of the study without major protocol deviations. The PP analysis set will be used as supportive analysis for the endpoints. The following will be considered major protocol deviations:

- Major inclusion/exclusion criterion deviation
- Significant protocol non-compliance that may confound the study objective data (e.g., use of prohibited medications)

The list of subjects excluded from the PP analysis set will be determined prior to analysis. If the PP analysis set does not differ from the mITT analysis set, separate analyses will not be presented.

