- Use the bolus calculator to administer meal boluses for all meals when carbohydrates are consumed as well as to administer correction boluses, when desired. For meal boluses, subjects will estimate the grams of carbohydrates for each meal, enter the carbohydrate estimate into the bolus calculator, check and manually enter their BG value into the bolus calculator and administer their meal bolus. For correction boluses, subjects will check and enter their BG value into the bolus calculator and administer their correction bolus. The timing of the bolus delivery will be per each subject's typical dosing routine.
- Consume meals and snacks of their own choosing.
- Subjects may adjust their basal rates or use advanced features such as Temp Basal and Extended Bolus per usual
- Follow their pre-exercise management such as insulin reduction for meal boluses, consumption of snacks, or adjusting their insulin delivery settings
- Treat themselves per their usual routine if they become hypoglycemic or hyperglycemic or have symptoms of either at any time during the study
- Change their CGM per manufacturer's instructions or sooner if necessary
- Change the Pod at least once every 72 hours
- For subjects aged 2-5.9 years of age, parents or trained caregivers will be instructed that they need to be physically present during the decision and delivery of insulin boluses for this age group, as well as be available for glucose monitoring and treatment during the 4-hour post bolus period.

Subjects and caregivers will be reminded to NOT use the system in Automated Mode for the duration of the 14-day study. Any use of automated mode will be considered a protocol deviation.

Subjects not currently enrolled in the Omnipod Horizon™ Pivotal Study (G190270) will be provided, by the site, information regarding treatment of hypoglycemia and hyperglycemia including sick day management and emergency management of severe hypoglycemia and diabetic ketoacidosis. Instructions will be given to subjects on how to contact clinical study staff 24-hours per day to report any study related problems. Subjects will be encouraged to call the clinical study site at any time with any concerns.

8.1.2 Visit 3

Visit 3 will be conducted either over the telephone or in person at the clinical study site on Day 3 ±1d. This visit will include:

- Review of concomitant medications
- Assessment of adverse events
- Assessment of complaints and/or device deficiencies

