10.4 Reportable Device Issues

Device complaints and device malfunctions will be reported except in the following circumstances. These occurrences are expected and will not be reported on a Device Deficiency Form:

- CGM sensor, transmitter or Pod lasting fewer days than expected per manufacturer
- CGM tape or Pod adherence issues
- Battery lifespan deficiency due to inadequate charging or extensive wireless communication
- Intermittent device component disconnections/communication failures not requiring system replacement or workaround/resolution not specified in user guide/manual.
- Device issues clearly addressed in the user guide manual that do not require additional troubleshooting

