11.5.1 Calculation of Percentage of Time in Range

Several effectiveness endpoints involve calculation of percentage of time in a specific glycemic range, including primary endpoints. These endpoints will be based on the direct output from a device (either a CGM or The Omnipod Horizon™ Automated Glucose Control System). The percentage of time in range (TIR) will be calculated as:

$$100 \times \frac{\text{\# of CGM records in range}}{\text{\# of evaluable CGM records}} = \text{TIR\%}$$

The following CGM records will be excluded from analysis, and therefore, from calculation of TIR endpoints:

- No glucose value is provided in the device output, such as due to an error or device deficiency during which the device does not record glucose readings

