11.8 Missing Data

All practical monitoring and follow-up steps will be taken to ensure complete and accurate data collection. All analyses will be based on available data only; no imputation for missing data is planned.

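### Should the per-protocol set also require a minimum amount of Phase 1 CGM data?

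*Combined protocol and SAP*

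**What the plan says.** Section 11.4.3 makes PP a subset of mITT. Subjects qualify if they "have a minimum of 80% system use (approximately 5.6 days) during Phase 2 of the study without major protocol deviations". The term system use is not defined. Two kinds of major deviation are listed: an eligibility deviation, and "Significant protocol non-compliance that may confound the study objective data". The second is not tied to either phase. PP is labelled supportive, its exclusions are to be settled before analysis, and it is not reported separately if it coincides with mITT.

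The mITT set (11.4.2) requires only successful entry into Phase 2. For the primary endpoints, section 11.3.2 states: "Glucose metrics during the 4-hour post bolus period from Phase 2 will be compared to Phase 1". Section 11.3.4 does the same for the secondary endpoints, per subject. Section 11.5 names paired or two-sample t-tests, with a signed rank test as fallback, and mentions no weights.

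Percent time is a ratio over evaluable CGM records (11.5.1). The one stated reason for removing a record is "No glucose value is provided in the device output, such as due to an error or device deficiency", and no minimum count is given. Section 11.8 adds: "All analyses will be based on available data only; no imputation for missing data is planned".

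**The concern.** A Phase 2 minus Phase 1 difference is only as good as the weaker of its two halves, and PP puts a number on one half only.

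The non-compliance clause would catch a subject who neglected the sensor in Phase 1. It would not obviously catch one who complied and lost data anyway, and the plan foresees such loss. Section 10.4 lists "CGM sensor, transmitter or Pod lasting fewer days than expected per manufacturer" and says of that list: "These occurrences are expected and will not be reported on a Device Deficiency Form". A subject with one or two usable Phase 1 days could enter Phase 2, meet the 80% rule and remain in PP.

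At stake is whether the supportive analysis is a sound check on mITT. The youngest cohort matters most: it has five subjects, endpoints are summarised by cohort, and ages 2-5.9 are expected to enrol after ages 6-70 finish, with two separate reports.

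**Working it through.** **Inputs.** Two phases of 7 days each (5.2). PP threshold 80% (11.4.3). Planned cohorts of 15, 10 and 5 evaluable subjects (11.2). Visit 2 on Day 1 and Visit 4 on Day 8 ±1 (Table 1, 8.2.1). The documents give no variances, so the precision figures below are an illustration.

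**The plan's own figure.** 0.80 × 7 = 5.6 days, as stated.

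**Weight of one subject.** In an unweighted paired mean this is 1/n: 1/15 = 6.7%, 1/10 = 10%, 1/5 = 20%. That sparse subjects carry full weight is inferred from the named tests; the plan does not say so. A subject with no Phase 1 data at all drops out of a paired test, so the issue is sparse data, not absent data.

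**Variance of one subject's difference.** Assume independent days of equal variance, 7 Phase 2 days and d Phase 1 days. In units of the daily variance, the within-subject part is 1/d + 1/7, and a full record gives 2/7. The ratio r to a full record is:

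- no between-subject variance in the effect: r = (1/d + 1/7) / (2/7)
- between-subject variance equal to 2/7: r = (1/d + 3/7) / (4/7)

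**Effect in the n=5 cohort.** With one sparse and four full subjects, the standard error (SE) relative to five full records is √((4 + r)/5). Dropping the sparse subject gives √(5/4) = 1.118, an 11.8% increase.

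| Phase 1 days | r (none / with between-subject variance) | SE increase if kept | SE increase if dropped |
|---|---|---|---|
| 1 | 4.0 / 2.5 | 26% / 14% | 11.8% |
| 2 | 2.25 / 1.63 | 11.8% / 6.1% | 11.8% |
| 3 | 1.67 / 1.33 | 6.5% / 3.3% | 11.8% |
| 5.5 | 1.14 / 1.07 | 1.4% / 0.7% | 11.8% |

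**Break-even.** Keeping and dropping are equal when (4 + r)/25 = 1/4, so r = 2.25. This gives d = 2.0 days without between-subject variance and d = 7/6 = 1.17 days with it. Between that point and 5.6 days, a 5.6-day floor excludes subjects whose retention would have given the smaller SE.

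**Fit with the visit window.** Phase 1 may run 6 to 8 days (Day 7 − 1 to Day 9 − 1). A fixed 5.6 days is 5.6/6 = 93% of the shortest permitted Phase 1 and 5.6/8 = 70% of the longest. A subject with 5.5 usable days out of 6 would fail despite following the schedule.

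**The case for a change.** The best case for a change is that one sentence would close the gap at almost no cost: no new data, mITT untouched, and a number fixed in advance instead of a judgement made when PP exclusions are listed. Phase 1 loss may also be harder to notice. The controller stores CGM readings only when a transmitter is connected (12.2.1), the data portal shows time in range with a connected CGM (section 3), and the data reviews at Visits 3 and 4 are aimed at bolus delivery, not sensor completeness. With one Phase 1 day, the n=5 SE does rise by 14% to 26%.

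It stands that no Phase 1 number exists and that one very sparse record could matter in the smallest cohort. The step to a rule is weaker.

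- The 80% reads naturally as an exposure rule for the phase in which the tested feature is used. A Phase 1 floor on CGM records would be a different kind of criterion, and would leave Phase 2 on undefined system use.
- The harm shown is loss of precision, and the floor makes that worse over most of its range. No reason is given why device-related loss would shift the Phase 2 minus Phase 1 difference.
- A whole-phase floor does not guarantee data in the 4-hour post-bolus windows that the primary endpoints use.
- Long gaps are already guarded against. Subjects receive sensors in the plural and are told: "Change their CGM per manufacturer's instructions or sooner if necessary". Section 11.8 commits to practical steps for complete data collection.
- Section 11.1 already provides subject data listings, so an analyst can see thin Phase 1 data. A separate listing of evaluable records by subject and phase would be harmless, but it adds reporting detail and changes no result.

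**Conclusion.** The observation is accurate, but no change is needed. PP has a numeric minimum for Phase 2 only, and a compliant subject with sparse Phase 1 data could remain in it. Whether to keep or exclude such a subject is a fair trade-off. In the five-subject cohort, exclusion improves precision only below about 1.2 to 2 usable Phase 1 days; from there up to 5.6 days it costs more than it saves, and it can remove subjects who used a permitted visit window.

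These figures assume independent days of equal variance, a full Phase 2 record, and between-subject effect variance from zero up to the full-record variance. They carry over to the post-bolus windows only if those are lost in proportion. How often Phase 1 data will be sparse cannot be judged from the documents.

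The consequence is small in any case. PP is supportive, the study is non-powered (11.2), and section 11.5 states no hypotheses and rules out use of the endpoint results for clinical claims. The primary mITT analysis has no data minimum in either phase and would be unaffected.
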